3.2 Primary Outcome

Comparison of bronchial lining fluid levels of biomarkers/mediators (periostin, surfactant protein D (SPD), CCL18, CXCL13) in patients with IPF and sarcoidosis.

- Determination of level of significance in the levels of the bronchial mediators between IPF and sarcoidosis patients.

3.3 Secondary Outcomes

1. Comparing mediator levels between airway samples (nasosorption and, bronchosorption) within and across the 3 groups (probable IPF, sarcoidosis and healthy controls). Establish significance between groups and correlations across patient groups for sampling types.
2. Comparing mediator levels and mRNA (gene expression) in blood with airway mediator levels across the 3 patient groups, and assessing the degree of correlation.

3. Comparing mediator levels in airway samples and blood with clinical parameters
4. Comparing urine metabolites across the 3 patient groups.

4 STUDY DESIGN AND SAMPLE COLLECTION

Any patients with probable IPF and sarcoidosis, who will be having bronchoscopy as part of their clinical diagnostic work up will be invited to have extra samples taken, including by the method of bronchosorption. However, the bronchosorption analysis results are not likely to benefit the individual subject.

Patients and healthy volunteers

Potential participants with probable IPF and Sarcoidosis having bronchoscopy as part of their clinical diagnostic work up will be identified by the study doctors and the Multi-Disciplinary Team (MDT) on the basis of inclusion/exclusion criteria. Patients who meet the inclusion and exclusion criteria will then be invited to participate in the study. Health controls will be recruited by approaching carers and partners of recruited patients as well as advertising in clinics, public places as well as local media.

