CXC	chemokine of cysteine -X- cysteine type
C3M	collagen degradation markers
CRPM	c-reactive protein degraded by MMP
DLco	diffusion factor for carbon monoxide
EL-M7	MMP-7 generated elastin fragments
FEV1/FVC	forced expiratory volume/forced vital capacity
GDPR	General Data Protection Regulation
KL-6	Krebs von den Lungen 6
IgE	immunoglobulin E
IL	interleukin
IPF	interstitial pulmonary fibrosis
MDT	multi-disciplinary team
MLF	mucosal lining fluid
MMP	matrix metalloprotease
MSD	Meso Scale Discovery
NAC	nasal allergen challenge
NS	nasosorption
SAE	serious adverse event
SAM	synthetic absorptive matrix
SP	surfactant protein
sRAGE	soluble receptor for advanced glycation end products

KEYWORDS

Idiopathic pulmonary fibrosis, biomarkers, mucosal lining fluid, nasosorption, bronchosorption, cytokines, chemokines,

STUDY SUMMARY

TITLE	FIBRO-SAM: Development of Airway Absorption Sampling Methods for Biomarker Assessment in Probable Idiopathic Pulmonary Fibrosis (IPF) Patients
DESIGN	Observational study with opportunistic airway sampling in patients with probable Idiopathic Pulmonary Fibrosis and Sarcoidosis, who are undergoing bronchoscopy as part of their diagnosis and/or monitoring
AIMS	To assess molecules reflecting pulmonary fibrosis using novel upper and lower airway sampling methods of absorption; nasosorption, (upper airway) and bronchosorption (lower airway).
OUTCOME MEASURES	Comparing levels of mediators including periostin, surfactant protein D (SPD), CCL18, CXCL13 in blood, nasal and bronchial airway mucosal lining fluid.
POPULATION	Probable Idiopathic Pulmonary Fibrosis patients (IPF) undergoing bronchoscopy, n = 30 Sarcoidosis patients, n = 15 Healthy volunteers, n = 15
ELIGIBILITY	Adults (aged 40 to 85 years) will need to meet inclusion and exclusion criteria. Patients in this study will be selected at the time of their scheduled clinical bronchoscopy at St Mary's Hospital at Imperial College Healthcare Trust and all Healthy controls will be recruited by approaching carers and partners of recruited patients as well as advertising in hospital OPA, public places and local media
DURATION	Clinical Phase: March 2020 to March 2021 (estimated)

Contents

1	INTRODUCTION	8
	Synthetic absorptive matrix (SAM):	9
	Nasosorption after nasal allergen challenge.....	9
	Bronchosorption:	9
2	STUDY SUMMARY	10
3	STUDY OBJECTIVE.....	12
3.1	Research Question and Hypotheses.....	12
3.2	Primary Outcome.....	12
3.3	Secondary Outcomes	12
4	STUDY DESIGN AND SAMPLE COLLECTION	13

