The total study involves a total of 30 subjects with probable IPF, 15 patients with sarcoidosis and 15 healthy volunteers. Recruitment for this study is likely to take between 12 and 24 months. An interim analysis at 12 months will be able to identify any emerging differences in biomarkers between the groups, and allow the nature of biomarkers of inflammation to be adjusted prior to the final analyses. In an exploratory study of novel methods of mucosal sampling in probable IPF and sarcoidosis, we do not know the rate of recruitment, and would prefer not to specify an exact number of patients for when interim analysis is performed.

Biomarkers to be measured:

1. Blood (serum) and MLF

There will be a particular focus on 4 biomarkers:
Periostin, surfactant protein D (SPD), CCL18 and CXCL13

A range of other biomarkers will be measured including the following:

- IL-1 β , IL-2, IL-8 (CXCL8), IL-12, IL-13, IL-17, IL-23, IL-33
- TGF- β , FGF basic, TNF- β , CTGF
- sICAM-1, sVCAM-1, CRP, SAA
- D-dimer and C3a, C5

Other biomarkers of inflammation may also be measured.

2. Whole blood for gene expression (mRNA) and DNA sequencing:

- To examine in peripheral blood expression of genes and or gene signatures related to IPF and disease progression
- To examine genetic loci that contribute to IPF risk and disease progression such as muc5b and TERT

3. Urine

- Collagen fragments and bioactive lipids involved in inflammation, which may include, but are not limited to C3M, pro-C3, CRPM, and EL-M7, may be measured.

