5.3 Inclusion criteria for Healthy Volunteers

- Age between 40 to 85 years, age and sex to match the group with IPF
- Healthy subjects without any diseases that may cause inflammation
- Women of childbearing age should not be pregnant, planning to get pregnant or breast-feeding.
- Currently non-smokers: see exclusion criteria

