5.4.2 Exclusion Criteria for Healthy Volunteers

- Current inflammatory/ immunological conditions. Any clinically significant diseases that may alter respiratory biomarkers: including respiratory, gastrointestinal, endocrine, haematological, cardiovascular, genitourinary, skin or neurological diseases.
- Recent or ongoing malignant diseases.
- Significant nasal anatomical defects preventing nasal sampling: including hypertrophy of turbinates, major septum deviation, nasal polyposis or recurrent sinusitis and nasal mucosal defects
- Upper respiratory tract infections in the past 6 weeks.
- Cigarette smoking:
 - no cigarettes in the last 2 weeks
 - not more than 10 cigarettes in the past year
 - <10 year lifetime pack history of smoking

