7.2.2 Schedule of assessments for healthy volunteers

Study procedures	Visit 1 at ICRRU, St Mary's Hospital, Paddington, London
	up to 3 hours
Inclusion and exclusion criteria	review
Blood for serum (10ml)	X
Urine	X
Whole blood for RNA (10ml)	X
Whole blood for DNA (5ml)	X
Nasosorption (left and right nostrils)	X

Sample Management

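### Blood relatives of recruited patients are not excluded from the healthy controls, so any IPF-versus-control comparison at inherited risk loci could be attenuated if relatives enrol (minor)

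*Combined protocol and SAP*

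**What the plan says.** Both the study summary table and section 4 name two routes to the 15 healthy volunteers: people close to the patients, and advertising. Section 4 reads "Health controls will be recruited by approaching carers and partners of recruited patients", and goes on to advertising, including in local media.

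Eligibility is set by age, sex and health. Section 5.3 asks for "Age between 40 to 85 years, age and sex to match the group with IPF" and for "Healthy subjects without any diseases that may cause inflammation". Section 5.4.2 begins with "Current inflammatory/ immunological conditions. Any clinically significant diseases that may alter respiratory biomarkers" and continues with malignancy, nasal defects, recent upper respiratory infection and smoking. Section 5.4.3 adds drug restrictions for all groups. None of these sections has a condition on kinship or family history.

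The schedule in 7.2.2 includes 5 ml of whole blood for DNA from each volunteer. Section 2 gives one purpose of the DNA work as "To examine genetic loci that contribute to IPF risk and disease progression such as muc5b and TERT".

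The primary outcome (3.2) compares bronchial fluid in IPF and sarcoidosis. Healthy volunteers enter the secondary outcomes (3.3) on airway mediators, blood mediators and mRNA, and urine. Neither 3.3 nor 8.3 specifies a genotype comparison.

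**The concern.** A study that looks at inherited risk loci needs a reference group whose genes are independent of the cases. These 15 volunteers are the only healthy reference in the study. A carer aged 40 to 85 may be a patient's sibling, or an adult child of an older patient, and would pass every listed criterion. Such a control carries the patient's risk alleles more often than an unrelated healthy person does, which pulls an IPF-versus-control difference towards zero. With so few controls there is little contrast to spare. The same could happen, more weakly, to a blood or nasal marker that is partly under inherited control.

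**Working it through.** The plan states no power, effect size or sample-size derivation (8.1), so there is no figure to reproduce. The check is on the direction and size of the effect.

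**Inputs from the documents:** 30 IPF patients, 15 sarcoidosis patients and 15 healthy volunteers (8.2); significance at P < 0.05 (8.3), taken as two-sided because sidedness is not stated.

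**Assumed, because the documents do not say:** the number of controls related to IPF patients, and all allele frequencies.

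**Formula.** Let p1 be the allele frequency in IPF cases, p0 that in unrelated healthy people, f the share of controls who are relatives of IPF cases, and r the fraction of the case's excess that a relative carries at an additive locus (first-degree 0.5, second-degree 0.25, unrelated partner 0). Then

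- expected frequency in controls = p0 + f × r × (p1 − p0)
- expected difference = (p1 − p0) × (1 − f × r)

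The proportional loss is f × r, which is f/2 for first-degree relatives.

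**All related controls are first-degree relatives of IPF cases:**

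- 3 of 15: f = 0.20, loss 0.20 × 0.5 = 10%
- 5 of 15: f = 0.333, loss 0.333 × 0.5 = 17%
- all 15: f = 1, loss 50%, the ceiling

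With second-degree relatives, 3 of 15 gives 0.20 × 0.25 = 5%. With unrelated partners the loss is 0 at any share.

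**Related controls split 2:1 between IPF and sarcoidosis families**, following the 30:15 group sizes (assumed). Relatives of sarcoidosis patients do not dilute an IPF contrast at IPF loci.

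- 3 related, of whom 2 to IPF cases: (2/15) × 0.5 = 7%
- 5 related, of whom 3.33 to IPF cases: (3.33/15) × 0.5 = 11%

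**What this does to power, as an illustration.** Take 60 case alleles against 30 control alleles, treated as independent, with a normal-approximation test of two proportions at two-sided 0.05.

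| Assumed p1 vs p0 | f = 0 | f = 0.2 | f = 0.5 | f = 1 |
|---|---|---|---|---|
| 0.20 vs 0.10 | 20% | 17% | 13% | 8% |
| 0.30 vs 0.10 | 57% | 47% | 33% | 16% |
| 0.40 vs 0.10 | 88% | 78% | 58% | 28% |

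**Markers in blood or nasal fluid.** If a share h of the group difference is inherited, the loss is f × 0.5 × h. At f = 0.2 this is 2% for h = 0.2 and 5% for h = 0.5 (both values of h assumed).

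**The case against.** The strongest reply is that the effect is conditional and touches only a side aim. Partners are normally unrelated to the patient, carers need not be kin, and advertising is a parallel source. Matching to the IPF group limits adult children. Requiring controls to be healthy means a related control carries slightly fewer risk alleles than the midway figure implies. No genotype comparison with controls is specified anywhere, so the arithmetic describes an analysis that the plan implies but does not set out. All of this stands. It makes the point minor but does not remove the gap in eligibility.

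Four stronger readings are tempting, and the documents do not support them:

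- *The case-control differences are biased.* A reader might infer this from the recruitment route. Bias arises only if relatives of IPF patients enrol, and their number is not given.
- *Carers and partners are approached first.* The text lists them before advertising but states no order or priority.
- *The effect could never be removed later.* Next of kin and contact details are collected from patients (7.1) and volunteers (7.2), and section 2 plans DNA sequencing of unstated extent. Many links could probably be traced. What is missing is a dedicated field and a planned check.
- *Shared households invalidate the unpaired tests in 8.3.* Shared exposures could narrow marker differences, for partners too, but the documents give nothing to size this. As for the tests, the variance of a difference is the sum of the two variances minus twice the covariance, so ignoring a positive patient-control correlation generally makes an unpaired test conservative. Household sharing is worth recording but does not carry this point.

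**Conclusion.** The point holds as a conditional weakness in control selection. Blood relatives of recruited patients are eligible as healthy controls in a study that takes the controls' DNA and examines IPF risk loci. If first-degree relatives of IPF patients enrol, an IPF-versus-control allele difference is attenuated by half their share of the control group: about 7% to 10% with 3 related controls and 11% to 17% with 5, depending on whether some belong to sarcoidosis families. These figures rest on an additive locus and on assumed counts. Secondary blood, nasal or mRNA contrasts are affected only as far as the markers are heritable, which the documents do not establish. The primary comparison of IPF with sarcoidosis is untouched. Severity is minor: a cheap improvement rather than a threat to the study's main conclusion.

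**What to change.** Add one line to 5.4.2 excluding any first- or second-degree blood relative of a recruited patient. Add one field to the volunteer's form for relationship to, and shared household with, any recruited patient. With relatives excluded, f = 0 and the attenuation from kinship disappears. Repeating the nasal and blood group comparisons without household members is an optional sensitivity analysis.

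The cost is one eligibility line and one form field. A few carers become ineligible, including relatives of sarcoidosis patients who would not affect the IPF loci. Unrelated partners and advertised volunteers remain available for the 15 places.

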4.1 Consent

Consent to enter the study will be sought after the patient has read and understood and had time to discuss the information contained within the Participant Information Sheet with friends and family. Signed participant consent will be obtained. The right of the participant to refuse to participate without giving reasons will be respected.

After the participant has entered the study the clinician remains free to give alternative treatment to that specified in the protocol at any stage if he/she feels it is in the participant's best interests, and the reasons for doing so should be fully documented. In such cases the participants remain in the study for the purposes of follow-up. All participants are free to withdraw at any time from the study without giving reasons and without prejudicing further treatment and care.

4.2 Patient Population

Patients diagnosed with probable IPF and Sarcoidosis will be included. Patients with probable IPF and Sarcoidosis will be selected from clinic lists for patients undergoing bronchoscopy as part of their clinical assessment, and they will be invited to participate in this study that involves additional sampling for clinical research purposes.

Probable IPF patients must have Usual Interstitial Pneumonitis (UIP) on CT scan and will be sub classified by gas transfer (DLco corrected for haemoglobin as detailed below;

- Mild (DLco>60)

- Moderate (DLco 40-60)
- Severe (DLco<40)

Healthy volunteers (age/sex matched, non-smoking, without a clinical history of atopy).

The patient populations will include:

- Probable Idiopathic Pulmonary Fibrosis (IPF), n=30
- Sarcoidosis patients, n=15
- Healthy Volunteers n=15

4.3 Sampling

For patients diagnosed with probable IPF and Sarcoidosis, BAL will be collected on the day of their scheduled bronchoscopy. Blood, nasosorption (NS), and bronchosorption (BS) samples will also be collected. Furthermore, on the day of their optional 3 and 6 months follow up visits, we shall collect blood and nasosorption (NS) samples. ***It is important to stress that bronchosorption samples must be taken before BAL or bronchial biopsy samples.*** All patients will have had HRCT of the lung and lung function testing (spirometry and DLco) up to 3 months before bronchoscopy sampling. Healthy volunteers will have a single visit with blood and NS sampling - but no bronchial samples.

With regard to possible coronavirus (COVID-19) infection, this clinical research project will meet Policies and Procedures in conjunction with the NHS, Imperial College London and Public Health England (PHE) guidelines. This will include use of Personal Protective Equipment (PPE) with appropriate clinical facilities and procedures. Appropriate precautions will be taken with sample collection, handling and processing.

5 ENTRY CRITERIA

5.1 Inclusion Criteria for Probable Idiopathic Pulmonary Fibrosis (IPF)

- Adult male or female patients aged 40 to 85 years
- Women of childbearing age should not be pregnant, planning to get pregnant or breast-feeding.
- Command of the English language to be able to give informed consent.
- **Probable IPF** requiring bronchoscopy to confirm the diagnosis, agreed within the local multi-disciplinary team (MDT), according to the American Thoracic Society/European Respiratory Society/Japanese Respiratory Society/ American Latin Thoracic Association (ATS/ERS/JRS/ALAT) guidelines (2018) (3)
- IPF disease diagnosis within the past 5 years
- Usual Interstitial Pneumonia (UIP) on HRCT scan.
- Recent lung function criteria:
 - Forced vital capacity (FVC) >40% of predicted value.
 - Carbon monoxide diffusing lung capacity (DLco) corrected for haemoglobin >30% of predicted value

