5.2 Inclusion criteria for Sarcoidosis

- Adult male or female patients aged 18 years and over
- Women of childbearing age should not be pregnant, planning to get pregnant or breast-feeding.
- Clinical symptoms, CT scan and biopsy diagnosis of sarcoidosis
- Patients with lung parenchymal disease and pulmonary stage II or more
- Recent lung function criteria
 - FVC > 50% predicted
 - DLCO > 40% predicted

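### The IPF group is enrolled and sampled on a provisional diagnosis, and no rule says how the primary contrast treats a patient whose final diagnosis is not IPF

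*Combined protocol and SAP*

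**What the plan says.** All references are to the combined protocol and SAP.

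- **Entry, IPF (5.1).** Patients have probable IPF "requiring bronchoscopy to confirm the diagnosis", with MDT agreement under the 2018 guideline. The same list requires "Usual Interstitial Pneumonia (UIP) on HRCT scan" and "IPF disease diagnosis within the past 5 years".
- **Entry, sarcoidosis (5.2).** "Clinical symptoms, CT scan and biopsy diagnosis of sarcoidosis" is required, so this label is not provisional.
- **Sampling (4.3, 7.1).** Samples are taken on the day of the scheduled bronchoscopy, and "bronchosorption samples must be taken before BAL or bronchial biopsy samples". The Introduction says that BAL fluid is examined to help diagnose lung disease.
- **Primary outcome (3.2).** Levels of periostin, SPD, "CCL18, CXCL13) in patients with IPF and sarcoidosis" are compared, with "Determination of level of significance in the levels of the bronchial mediators between IPF and sarcoidosis patients". Research question 1 (3.1) also asks about IPF patients.
- **Analysis (8.3).** The groups are named as probable IPF, sarcoidosis and healthy controls.
- **Final diagnosis.** The visit schedule (7.1.1) has no entry for it. The withdrawal rules (5.5, 9.1) cover side effects, withdrawn consent and loss of capacity, but not a changed diagnosis. Section 8.3 has no reclassification rule and no analysis in confirmed IPF.

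**The concern.** By the protocol's own wording the IPF diagnosis is still open when the patient enters and is sampled, whereas the comparator is biopsy-diagnosed. The question asked is about IPF, and the group named for analysis is probable IPF. These differ by the patients whose final diagnosis turns out to be something else, and the plan does not deal with them.

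Two things are at stake. First, if such patients stay in, the estimate describes a mixture and not IPF. Section 8.1 hopes to use these results to size future studies, so a biased difference would be carried forward. Second, if the team takes them out, it does so without a written rule. Section 8.2 plans a look at group differences at 12 months, so that choice could be made after biomarker results have been seen.

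**Working it through.** The plan has no power or sample-size figure to reproduce, because section 8.1 declines to give one. What follows is illustration.

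**Inputs from the documents.** 30 probable IPF and 15 sarcoidosis (4.2); P < 0.05 (8.3), taken as two-sided because sidedness is not stated.

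**Assumed inputs.** True IPF–sarcoidosis difference d = 1.0 SD on one mediator, within-group SD 1. The misclassified share m is 10, 20 or 30%. The misclassified patients' mean is placed by k: 0 = sarcoidosis mean, 0.5 = halfway, 1 = IPF mean, 1.5 = beyond IPF.

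**Formulas.**
- Expected difference = d(1 − m + mk).
- Variance in the IPF group = 1 + m(1 − m)d²(1 − k)².
- Power is for a pooled t-test, with standard-error factor √(1/15 + 1/30) = 0.316 for 30 v 15.

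**One case in full (m = 20%, k = 0).** Expected difference 1.0 × 0.8 = 0.80. IPF-group variance 1 + 0.2 × 0.8 = 1.16. Pooled SD √[(14 × 1 + 29 × 1.16)/43] = 1.053. Standardised difference 0.80/1.053 = 0.76, and noncentrality 0.76/0.316 = 2.40. Power is about 65% by noncentral t and 66% by simulation.

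**Results (simulated; expected difference in SD, then power).** With no misclassification, power is 87%.

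| Not IPF | k = 0 | k = 0.5 | k = 1.5 | Confirmed only (d = 1.0) |
|---|---|---|---|---|
| 10% | 0.90, 78% | 0.95, 83% | 1.05, 90% | 27 v 15: 86% |
| 20% | 0.80, 66% | 0.90, 78% | 1.10, 92% | 24 v 15: 84% |
| 30% | 0.70, 53% | 0.85, 74% | 1.15, 94% | 21 v 15: 82% |

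The higher power in the k = 1.5 column is no gain, because it comes from overstating the IPF difference.

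**Check at a smaller effect.** The difference detectable with 80% power is (1.960 + 0.842) × 0.316 = 0.886 SD (normal approximation). With SD held at 1 and k = 0, power falls to 71, 61 and 50% at m = 10, 20 and 30%, against 79, 77 and 75% in confirmed patients only. The pattern is the same.

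**Effect on later planning.** At 80% power a two-sample t-test needs about 17 per group for 1.0 SD and about 26 for 0.8 SD. A dilution of that size would make a follow-on study about half as large again as it need be.

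**The case against.** The strongest reply is that entry is much tighter than mere suspicion. A patient needs UIP on HRCT, MDT agreement and an IPF diagnosis within 5 years. Section 5.4.1 excludes hypersensitivity pneumonitis and drug-induced, occupational, asbestos-related and connective-tissue disease. Probable IPF is used in the title, population, secondary outcomes, sample-size and analysis sections, so the bare IPF in 3.1 and 3.2 may be shorthand. Comparing patients as they present at bronchoscopy is a legitimate aim for an exploratory study of sampling methods, and no stated power is contradicted.

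Much of this stands. A reader might infer that the IPF arm is everyone once suspected of IPF; the entry criteria rule that out, and the misclassified share may be small. A reader might also infer that the plan keeps patients with another final diagnosis. It does not say so: retention follows by default from silence, and removal is equally unwritten.

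Two parts do not answer the point. Section 5.1 itself still requires bronchoscopy to confirm the diagnosis, so some changes must be expected. The 5-year criterion does not settle the matter either, because it sits uneasily with a diagnosis still awaiting confirmation. If the as-presenting population is the intended one, 3.1 and 3.2 should say so.

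**Conclusion.** The concern holds as an undefined analysis population for the primary contrast. Entry and sampling use a provisional label, the outcome is worded for IPF, and nothing connects the two once the bronchoscopy result is known. Followed as written, a patient found not to have IPF is analysed as IPF.

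The direction of bias is probably towards a smaller difference. It is tempting to call dilution certain, but the documents do not support that: it requires the misclassified patients' levels to lie towards sarcoidosis, and nothing in the plan says where they lie. The sarcoidosis-mean figures (66% power at 20%) are the low end of the cases shown. The halfway case (78% against 84%) is a modest loss, and a mean beyond IPF inflates the difference to 1.10 SD at 20%.

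These sizes rest on an assumed effect, SD, misclassified share and misclassified mean. They also apply to each of the four mediators singly, without allowance for multiplicity. The confirmed-only column assumes that the final diagnosis is correct and available for everyone. No figure in the plan is wrong. This is a worthwhile and inexpensive improvement, not a fatal flaw.

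**What to change.** - Record the final post-bronchoscopy MDT diagnosis for both patient groups, by people blind to biomarker results. Fix it before the baseline biomarker data are analysed, including for the 12-month interim look.
- Do not tie the deadline to the 6-month visit, because section 4.3 makes the follow-up visits optional. Baseline samples are shipped only once all have been collected (7.9, 10.1), so there may be time, but the plan does not say when the MDT concludes.
- In 3.2 and 8.3, define the primary analysis groups by that diagnosis. Report how many patients are reclassified or unresolved, and show other final diagnoses descriptively.
- Keep the as-enrolled contrast as a sensitivity analysis. Report any ROC analysis in the as-enrolled set as well, since confirmed cases alone may make discrimination look better than in the patients who actually present.
- Reconcile the criteria "IPF disease diagnosis within the past 5 years" and "requiring bronchoscopy to confirm the diagnosis" in 5.1.

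**Cost.** One case-report field and some protocol wording, assuming the MDT reaches a diagnosis after bronchoscopy in routine care. The downsides are a slightly smaller IPF group, some patients possibly without a final diagnosis, and a more selected group for ROC estimates.
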